6.2.4 Follow-up visits and other data collection

Follow-up assessments at 3 and 6 months include the following (all described above in the baseline assessment section):

- Blood draws/laboratory tests
- Weight measurement
- Computerized tests of behavioral impulsivity and cognitive tasks
- Health history/medication changes
- Online battery of self-report questionnaires; may be completed at in-person visit if preferred (described above)
- 24-hour dietary recall
- Craving EMA

We aim to complete the 3 and 6 month visits with all participants within a 2-3 week window at these timepoints.

At-Home Ketone Monitoring: Participants will be given a home ketone monitoring device (Precision Xtra® System) and ketone strips, which measure beta-hydroxybutyrate. This is a glucometer device that also measures ketones from finger-stick blood if ketone strips are inserted instead of glucose

strips. The device store data, which will be checked periodically during class sessions to confirm accuracy of self-reported measurements. *Frequency:* Participants will be asked to measure ketones before dinner 3 times a week for approximately 4 weeks during the intervention (to provide more intensively self-monitoring when starting the diet) and twice weekly thereafter to monitor ketosis/diet adherence. We will use the EMA system to send requests to check ketone levels and report values back. During study visits, participants will be asked to bring in the meter and staff will download data on devices to provide a check on accuracy of participant reported measures.

6.2.5 Completion/Final Evaluation

The assessments to be performed at the final evaluation are listed above (section 6.2.4).

The only potential reason for early termination that we anticipate are participant-driven, including having to move out of the Bay Area, or dislike of/unwillingness to continue to follow the study diet. We will take steps to help participants implement the study diet in a way that works well for them, in order to prevent these kinds of early terminations. Participants who experience a life event (e.g. job change, family crisis) that affects their ability to continue to attend the intervention classes will be encouraged to continue to follow the study diet and other intervention steps to the best of their ability. They will be offered course materials and handouts in order to facilitate their ability to maintain behavioral changes that they made to date. Participants who discontinue the study intervention early will be asked to remain in the study and complete follow-up assessments as originally planned. If a participant moves out of the Bay Area or otherwise is unable or unwilling to come for a study follow-up visit, study staff will work with them to complete questionnaires online and have a blood draw at a LabCorp location convenient to them.

7. SAFETY ASSESSMENTS

7.1 Specification of Safety Parameters

The key study intervention involves diet changes, which in general is a minimal risk intervention step. The risk of hypoglycemia in persons receiving medications such as insulin or sulfonylureas is a possible serious potential adverse event, however. We anticipate that with the precautions described in detail below, the risk of serious hypoglycemia will be very low. While we encountered no serious adverse events in pilot testing, there has been little careful long-term assessment of adverse events with carbohydrate restricted diets in T2DM, which means there is some uncertainty in predicting the likelihood of adverse events. Other anticipated risks include those associated with venipuncture, psychological testing, and loss of confidentiality. None of these risks are anticipated to occur at a frequency exceeding 5%.

Expected risks to the subject from the carbohydrate-restricted diet are as follows:

1. *Hyperlipidemia:* There have been reports this approach, which involves increases in proportion of calories from fat, causing increases in LDL cholesterol, a risk factor for heart disease. However, several clinical trials of carbohydrate restricted diets for obesity, including three of up to one-year duration, have not shown this relationship:

We will monitor serum fasting lipid profiles at baseline, 3, and 6 months (also 12 months in R33 phase) to assess this potential risk.

2. Hypoglycemia: The carbohydrate restricted diet may lead to decreases in glucose levels. In persons receiving medications such as sulfonylureas or insulin, this could increase the risk of hypoglycemia if appropriate medication adjustments are not made while the participant is transitioning into nutritional ketosis (once in nutritional ketosis, beta-hydroxybutyrate as a preferred CNS fuel offers some protection against symptomatic hypoglycemia.⁵⁶). In our pilot study, we used a medication reduction algorithm that resulted in no episodes of hypoglycemia. For the proposed study, we will use a similar algorithm.

Initial HbA1c	Initial medication reduction
6.5-7.0%	
 • Continue: Metformin, TZD • Reduce by 50%: Basal insulin • Stop: Secretagogue, prandial insulin, pre-mixed insulin, acarbose, GLP-1 ag/DPP4 inhibitor
7.1-8.0%	
 • Continue: Metformin, TZD • Reduce by 50%: Basal insulin, pre-mixed insulin, secretagogue, GLP-1 ag/DPP4 inhibitor • Stop: Acarbose, prandial insulin
8.1-12%	
 • Continue Metformin, TZD, secretagogue, basal insulin, GLP-1 ag/DPP4 inhibitor • Reduce by 50%: Pre-mixed insulin, • Stop: Acarbose, prandial insulin

TZD: thiazolidinedione; secretagogue: sulfonylureas and meglitinides; GLP-1 ag: glucagon like peptide 1 agonist; DPP-4 inhibitor: dipeptidyl peptidase 4

For the first 6 weeks of the trial, participants on non-insulin medications will be asked to check blood glucose (BG) fasting and pre-dinner. If taking insulin, participants will be asked to check BG before each injection (standard of care). BGs will be reviewed on a weekly basis by study physicians, including an endocrinologist. If the majority of BG values drop below 110, or there are other concerning BG patterns, we will reduce/stop medications in the following order:

1. Pre-mixed insulin
2. Secretagogue
3. GLP-1 ag/DPP4 inhibitor
4. Basal Insulin

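### Section 7.1 schedules home glucose checks for secretagogue users not on insulin only through week 6, although the drug and the step-down rule can run on and section 6.1 sets no week limit

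*Combined protocol and SAP*

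**What the plan says.** Section 7.1 of the combined protocol and SAP names insulin and sulfonylurea users as the people for whom hypoglycemia is a possible serious event. Its precautions are:

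- **Starting dose.** A secretagogue is stopped at HbA1c 6.5-7.0%. At 7.1-8.0% it is halved: "Reduce by 50%: Basal insulin, pre-mixed insulin, secretagogue, GLP-1 ag/DPP4 inhibitor". At 8.1-12% it stays at full dose: "Continue Metformin, TZD, secretagogue, basal insulin, GLP-1 ag/DPP4 inhibitor".
- **Home checks.** "For the first 6 weeks of the trial, participants on non-insulin medications will be asked to check blood glucose (BG) fasting and pre-dinner". For the other risk group: "If taking insulin, participants will be asked to check BG before each injection".
- **Step-down rule.** Study physicians review the readings weekly. Drugs are cut in a fixed order on this trigger: "If the majority of BG values drop below 110, or there are other concerning BG patterns". The secretagogue is second in that order, after pre-mixed insulin. Neither the review nor the rule has an end date.
- **Rationale.** The added risk arises "if appropriate medication adjustments are not made while the participant is transitioning into nutritional ketosis", and ketosis itself "offers some protection against symptomatic hypoglycemia". Of the pilot it reports: "we used a medication reduction algorithm that resulted in no episodes of hypoglycemia".

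The schedule in section 6.1 has a row for home glucose monitoring, marked once under Intervention Period. It gives no weeks, frequency or drug group. Section 5.1 sets 12 weekly classes.

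**The concern.** The step-down rule acts on glucose readings. On the 7.1 wording, the scheduled readings stop by calendar, not when the secretagogue stops. Nothing in the plan says the drug must be off by week 6, or that the move into ketosis is complete by then. A participant could spend the second half of the course on a drug the plan itself links to hypoglycemia, with the rule still nominally in force but no scheduled value to trigger it. A cut would then depend on a reported symptom, an unscheduled reading, or the physicians' weekly review of other information.

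Symptoms may be a weaker signal here. If ketosis protects against symptomatic hypoglycemia, a low value might be noticed less often. That is an inference, not something the plan states.

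**Working it through.** No figure in the plan needs reproducing. The check is a comparison of the relevant sections and a short count.

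**Who is affected.** Participants who take a secretagogue, take no insulin and start at HbA1c 7.1% or above. The drug is kept in 2 of the 3 bands (7.1).

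**What is scheduled for them in weeks 7-12:**

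| Source | Weeks 1-6 | Weeks 7-12 |
|---|---|---|
| 7.1 home glucose | Fasting and pre-dinner | None stated |
| 6.1 home glucose row | Marked, no frequency | Marked if the row covers the whole period; no frequency |
| 6.2.2 laboratory fasting glucose and HbA1c | Baseline only | None until the 3-month follow-up; not tied to the below-110 rule |
| 6.2.4 home ketones, before dinner | 3 a week for about 4 weeks, then 2 a week | 2 a week |

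**Two readings of the text.**

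1. If 7.1 governs, there are 0 scheduled home glucose readings for this group in weeks 7-12. If the weekly review and the rule end with the 6-week window, no glucose-based step-down remains. If they continue, they have no scheduled input.
2. If 6.1 covers all 12 weeks and 7.1 sets only the early intensity, some monitoring is intended after week 6, but its frequency is not stated.

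Either way, the plan does not tell staff what to ask of these participants after week 6.

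**Finger-sticks already in place.** Section 6.2.4 supplies a glucometer that also reads ketones.

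- Ketone checks in weeks 7-12: 2 per week × 6 weeks = 12.
- Over the course: 3 × 4 + 2 × 8 = 28, approximate because the length of the first stage is approximate.

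One glucose strip at each of the later checks is therefore 12 extra strips per affected participant. Twice-daily checks would need 2 × 7 × 6 = 84, which is 84 / 12 = 7 times as many. That figure assumes daily testing, which 7.1 does not state outright.

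**Number affected.** The documents give no count or proportion of participants on a secretagogue without insulin, so none is computed. For n such participants the cost is 12n strips; for example, 10 participants would need 120.

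**The case against.** The strongest reply is that the 6-week window is a reasoned choice. The plan places the added risk in the transition, and a similar algorithm produced no hypoglycemia in the pilot. With no insulin to cut, the secretagogue is in effect the first drug reduced. Anyone still on it at week 6 has passed six weekly reviews without the rule removing it. Other safeguards then continue: weekly review of symptoms and medication adjustments, the phone line and pager, contact with primary care, the core team's weekly safety review (7.6), hypoglycemic episodes solicited at visits (7.3), and fasting glucose and HbA1c at 3 months. Insulin users have their own checks. All of this stands, and it makes the residual risk probably small. It does not give the below-110 rule a scheduled reading.

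The second reply is that 6.1 may already cover all 12 weeks. That reading is fair. A reader might infer from 7.1 alone that the plan definitely schedules nothing after week 6. The documents do not support so firm a statement, because the 6.1 row has no week limit. What they support is a mismatch, with no frequency stated after week 6 on either reading.

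A reader might also infer that later lapses from and returns to ketosis, which the resilience outcome in 1.2 and 9.5.2 anticipates, repeat the original risk. That outcome concerns ketones and says nothing about glucose or hypoglycemia, so the link is inference. A returning participant would normally be on the same dose or a lower one.

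**Conclusion.** The point holds as a mismatch between 6.1 and 7.1 and a gap on the 7.1 wording. For secretagogue users not on insulin, in two of the three HbA1c bands, the step-down rule can lose its scheduled home readings for 6 of the 12 course weeks. It does not show that participants are being harmed or that hypoglycemia after week 6 is likely. The documents do not say how often glucose falls further after week 6, or how many people are affected.

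The conclusion assumes that some participants remain on the drug past week 6, which the plan permits but does not quantify. It also assumes that the 7.1 sentence, as the only text giving a week count, is what staff would follow. This is a cheap improvement to patient safety, not a flaw that undermines the trial.

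**What to change.** In 7.1, replace the timing sentence with wording such as:

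> Counting from the first weekly class, participants on non-insulin medications check glucose fasting and pre-dinner in weeks 1-6. Anyone still taking a secretagogue after week 6 also takes a glucose reading at each twice-weekly pre-dinner ketone check, until the drug is stopped or at least through week 12. Weekly physician review and the below-110 or concerning-pattern rule apply for as long as checks run.

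In 6.1, annotate the home glucose row to match: weeks 1-6 for participants on non-insulin medications, weeks 7-12 for those still on a secretagogue.

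The cost is a wording amendment, about 12 strips per affected participant and a few minutes of physician review a week. It needs no new device and no extra test session.

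This is a minimum. With two readings a week, a majority below 110 means both, although the concerning-pattern clause still lets a physician act on one. Pre-dinner values do not show fasting glucose, so the investigators may prefer to add fasting checks. Week 12 is a practical minimum because the weekly classes end there and the 3-month visit follows. They may extend it into maintenance for anyone still on the drug.

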4. SELECTION AND ENROLLMENT OF PARTICIPANTS

4.1 Inclusion Criteria

Participants must meet all of the inclusion criteria to participate in this study:

1. History of T2DM mellitus. If taking insulin, screening labs will include C-Peptide to rule out T1DM. The study intervention is not designed for people with Type 1 diabetes who make no insulin.
2. HbA1c > 6.5% and < 12.0% at screening. The lower limit confirms the diabetes diagnosis. Persons with a HbA1c > than 12% typically need immediate attention to the medical regimen, and we aim to have this done before entering the trial to better separate the effects of improved medical regimens from the diet intervention. Potential participants with a HbA1c > 12% can be enrolled once glucose control is improved.
3. Experience food-related cravings most days of the week and eat in response to these cravings regularly. A key hypothesis is that our mindfulness approach will reduce cravings and craving-related eating, and this is primary mechanistic outcome. Thus we need to recruit participants who experience this.
4. Aged 18 years old and older. We are not enrolling younger children as they may need an intervention that is better tailored to children.
5. Able to engage in light physical activity. We will be recommending physical activity as part of the intervention.
6. Willing and able to participate in the interventions. Must be interested in following a carbohydrate- restricted diet, willing to learn about mindful eating and behavioral strategies for following prescribed diets, have sufficient control over their food intake so that they can follow either diet, and otherwise be able and willing to participate in the intervention. Intervention content must be practiced to evaluate whether it is effective.
7. Have smartphone and are willing to use it on a regular basis for data collection (e.g. craving EMA assessment).
8. Ability to speak English. Groups will be conducted in English, and we do not have the capacity, given the resources available in this proposal, to translate all course material and conduct groups into another language. We enrolled Hispanic participants into the pilot study who were fluent in English, and expect to do this in the proposed study.

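### Section 7.1 ties insulin users' glucose checks only to injections, so a once-daily basal-only user (assumed) is checked at one time of day, against two for participants on non-insulin medications

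*Combined protocol and SAP*

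**What the plan says.** Insulin users are eligible. Section 4.1 says "If taking insulin, screening labs will include C-Peptide to rule out T1DM". Section 7.1 names them among those at risk: "The risk of hypoglycemia in persons receiving medications such as insulin or sulfonylureas is a possible serious potential adverse event, however".

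Section 7.1 then sets two home-monitoring rules for the first 6 weeks. Under one, "participants on non-insulin medications will be asked to check blood glucose (BG) fasting and pre-dinner". Under the other, "If taking insulin, participants will be asked to check BG before each injection (standard of care". Study physicians review the values weekly and reduce or stop drugs in a set order "If the majority of BG values drop below 110, or there are other concerning BG patterns".

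The table in the same section sets the starting drug changes by HbA1c band:

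- Prandial insulin is stopped in all three bands. The 6.5-7.0% entry reads "Stop: Secretagogue, prandial insulin, pre-mixed insulin, acarbose, GLP-1 ag/DPP4 inhibitor" and the two higher bands read "Stop: Acarbose, prandial insulin".
- Basal insulin is halved in the two lower bands and continued in the 8.1-12% band. It is never stopped at the start.

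No other section supplies check times. Section 6.1 marks home glucose monitoring in the intervention period without a frequency, and the home-testing schedule in Section 6.2.4 is for ketones.

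**The concern.** The number and timing of an insulin user's checks depend entirely on the injection regimen, and the protocol's own table removes injections. A basal-plus-prandial user loses the prandial doses, and the checks attached to them, as the diet begins. Section 7.1 describes that transition as the period when hypoglycemia risk rises if medication is not adjusted.

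A participant on metformin alone is therefore asked for checks at two times of day, while one on once-daily basal insulin alone is asked for checks at one. Both limbs of the weekly review, the majority rule and the pattern clause, can use only values that were collected. A symptom-free fall at an unchecked time enters neither. Hypoglycemic episodes are also solicited at study visits (Section 7.3), but the first follow-up visit is at 3 months, after the 6-week window has closed.

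**Working it through.** The plan states no weekly number of glucose values, so there is no figure to reproduce.

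**Inputs.** From Section 7.1: two check times for participants on non-insulin medications, one check per injection for insulin users, a 6-week window (42 days) and weekly review (7 days). Assumed: the fasting and pre-dinner checks are daily, which the text implies but does not write; basal insulin is injected once daily, with twice daily as the alternative. The documents give no injection frequencies and no number of insulin users.

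**Step 1: values collected.** Values per week = checks per day × 7. Six-week total = checks per day × 42.

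| Regimen | Checks/day | Per week | 6 weeks |
|---|---|---|---|
| Non-insulin medications | 2 | 14 | 84 |
| Basal alone, once daily | 1 | 7 | 42 |
| Twice-daily injections | 2 | 14 | 84 |
| Once-daily basal plus oral drug, injection rule replaces the other | 1 | 7 | 42 |
| Same, both rules apply, morning dose | 2 | 14 | 84 |
| Same, both rules apply, bedtime dose | 3 | 21 | 126 |

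A participant who starts on basal plus three prandial doses a day (assumed) goes from 4 × 7 = 28 checks a week to 7 once prandial insulin is stopped.

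**Step 2: what the weekly review would see, for basal insulin alone once daily.** A floor means fasting and pre-dinner checks each day at minimum.

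| Case | Low values now | With the floor, pooled |
|---|---|---|
| A. Morning dose, only fasting values below 110 | 7 of 7, majority met | 7 of 14 = 50%, not a majority |
| B. Morning dose, only pre-dinner values below 110 | 0 of 7 | 7 of 14 = 50%, not a majority |
| C. Bedtime dose, only fasting values below 110 | 0 of 7 | 7 of 21 = 33%, not a majority |

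In B and C the physicians now have no low value to act on. With the floor they have seven, all at one time of day. The majority rule still does not fire, so the gain comes through the pattern clause. In A the floor dilutes the majority rule, and the pattern clause has to cover that case too.

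**Step 3: how often a majority is reached.** Suppose each value is independently below 110 with chance p = 0.3, 0.4 or 0.5 (assumed range).

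- One check time, P(Bin(7, p) ≥ 4): 0.126, 0.290, 0.500.
- Two times pooled, P(Bin(14, p) ≥ 8): 0.031, 0.150, 0.395.
- Two times judged separately, 1 − (1 − P(Bin(7, p) ≥ 4))²: 0.236, 0.496, 0.750.
- Three times judged separately, 1 − (1 − P(Bin(7, p) ≥ 4))³: 0.332, 0.642, 0.875.

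One person's readings are correlated. At full correlation between times, the separate-time figures fall back to the one-time figures.

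**The case against.** A check before every injection is a minimum scaled to the regimen, and the protocol calls it standard care. Physicians, including an endocrinologist, review values weekly and can act on patterns, so the 110 majority is not the only trigger. Symptoms are reviewed weekly, and there is a study phone line with pager access to physicians. Doses are cut at the start, and of the pilot the protocol reports: "In our pilot study, we used a medication reduction algorithm that resulted in no episodes of hypoglycemia". Any finger-stick schedule leaves some hours unchecked.

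Most of this stands, and it keeps the point minor. It does not remove the point, because no safeguard supplies a value at an unchecked time when there are no symptoms. Starting reductions also do not reach every basal user, since the highest HbA1c band continues basal insulin, though from higher glucose. The pilot algorithm is described as similar, but its checking schedule and number of insulin users are not given.

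Three stronger readings are tempting and not supported:

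- *Insulin users as a class are monitored less.* Twice-daily injectors match the other group in number. A participant on basal insulin plus metformin plausibly falls under both sentences and then has no shortfall.
- *Fewer values make the trigger less sensitive.* At equal p, Step 3 shows the reverse: 13%, 29% and 50% of weeks with one check time, against 3%, 15% and 40% with two pooled. What is missing is coverage of the day.
- *The rule should fire automatically on a majority at any one check time.* That would raise twice-daily injectors, who have no shortfall, from 3%, 15% and 40% of weeks to 24%, 50% and 75%, and bedtime basal users from 13%, 29% and 50% to 33%, 64% and 88%. It would reduce medication at a threshold that is not hypoglycemia, with HbA1c and fasting glucose among the secondary outcomes. Limited to insulin users, it would also omit sulfonylurea users, whom Section 7.1 names beside them.

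**Conclusion.** The gap is real but narrow. Followed as written, Section 7.1 collects 7 values a week at one time of day from a once-daily basal-only participant, against 14 at two times from a participant on non-insulin medications (42 against 84 over 6 weeks). With a bedtime dose, neither a fasting nor a pre-dinner value is asked for. This rests on once-daily injection, on daily checks in the comparison group, and on the participant taking no other glucose-lowering drug. It extends to basal-plus-oral users only if the injection rule replaces the other rule, which the text leaves open.

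A reader might infer that the plan would miss hypoglycemia. The documents do not show that: no missed episode can be estimated, and the size of the subgroup is not stated. The effect is confined to safety monitoring. It is a minor point, worth a cheap change of wording.

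**What to change.** Replace the two check sentences in Section 7.1 with: *For the first 6 weeks, every participant taking any glucose-lowering medication, including insulin, will check BG fasting and pre-dinner each day at minimum; participants taking insulin will also check before any injection given at another time.* This also settles which rule basal-plus-oral users follow.

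Leave the majority-below-110 rule unchanged and add no automatic per-time trigger. Add a note that a majority of values below 110 at one check time counts as a concerning pattern for the weekly review, with any reduction left to the physicians' judgment. The note covers case A, where pooling dilutes the majority rule. It need not be limited to insulin users.

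Costs:

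- Extra checks: none for people injecting before breakfast and dinner; 1 a day (1 × 42 = 42 over 6 weeks) for a morning basal-only user; 2 a day (2 × 42 = 84) for a bedtime basal-only user; none for basal-plus-oral users if both rules already apply.
- Glucose strips: the supplied ketone meter also reads glucose, but Section 6.2.4 mentions supplying ketone strips only.
- Some extra physician review, because the note will flag more weeks than the pooled rule does.

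The change adds no visits and applies equally in both arms.
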